Table 1. Study objectives and outcome measures	4
Table 2. Confidence intervals by observed proportion of responders	9
Table 3. Variables in the multiple imputation model	23

Abbreviations

AE	adverse event
CRF	case report form
FCS	fully conditional specification
HRQoL	Health-Related Quality of Life
ITT	intent-to-treat
MedDRA	Medical Dictionary for Regulatory Activities
mITT	modified intent-to-treat
OAB	overactive bladder
OABq	Overactive Bladder Symptom Quality of Life Questionnaire
PGI-I	Patient Global Impression of Improvement Questionnaire
PP	per-protocol
PT	preferred term
PVR	post void residual
SAE	serious adverse event
SAP	statistical analysis plan
SCI	Statistics Collaborative, Inc.
SOC	system organ class
TEAE	treatment-emergent adverse event
TENS	transcutaneous electrical nerve stimulation
UUI	urgency urinary incontinence

1. Introduction

This statistical analysis plan (SAP), which is based on Version 3.6 of the study protocol dated August 27, 2019, defines the methods and analyses that Valencia Technologies Corporation (henceforth, Valencia) plans to use to analyze the data from Protocol G170301. If the protocol is subsequently amended, this SAP may be amended as well. If there are minor differences between the analyses described in the protocol and the analyses in the SAP, the analyses in the SAP will prevail.

2. Investigational plan

2.1. Study design

Valencia's protocol G170301 is a multicenter, single-arm study designed to evaluate the safety and effectiveness of eCoin™ tibial nerve stimulation in subjects with urgency urinary incontinence (UUI). Up to 135 subjects, with a target of 120 subjects, who meet all inclusion and exclusion criteria and have provided informed consent will be enrolled to participate. All subjects will be scheduled to receive the investigational therapy (eCoin™ for UUI).

The eCoin™ neuromodulation device will be implanted subcutaneously in the right or left leg of subjects. After a 4 week implant healing period, all subjects will have a programming visit during which the device will be activated (turned on). Subjects will be followed for 48 weeks post-device activation (equivalent to 52 weeks post-implantation). All subjects will be explanted after the final study visit at 48 weeks post-activation.

2.2. Long-term follow-up study

All subjects will be allowed to consent to extended follow-up. These subjects will not be explanted at 48 weeks post-activation, and will have the option to be followed for an additional 1 to 2 years. These subjects will be explanted shortly after their 96 week post-activation visit or their 144 week post-activation visit.

2.3. Overactive bladder (OAB) medications

All subjects are expected to remain free of pharmacological medications for overactive bladder (OAB), unless medically necessary, until the primary endpoint is measured at 48 weeks post-activation. Use of OAB medication is considered a minor protocol deviation. Subjects who are taking pharmacologic medication at screening should be washed off overactive bladder medications for a period of two weeks prior to the baseline visit.

2.4. Transcutaneous electrical nerve stimulation (TENS) protocol

A secondary motivation for this trial is to ascertain whether there is a relationship between responders to transcutaneous electrical nerve stimulation (TENS) and responders to eCoin™ therapy. Subjects will receive a TENS unit at baseline with instructions to perform TENS of the tibial nerve twice daily for seven days. Subjects will be asked to complete a voiding diary in the last three days of the TENS protocol. This TENS protocol will occur after the baseline visit but before implantation with eCoin™. Response or lack of response to the TENS protocol does not affect subject eligibility.

2.5. Eligibility criteria

See the protocol for eligibility criteria.

After enrollment for this study began, Valencia discovered that one center had implanted the eCoin™ neuromodulation device in several subjects who had not met the eligibility criteria. Valencia will implement further on-site training in an effort to prevent any additional subjects from being consented and enrolled in the study without meeting all eligibility criteria. Any subjects enrolled who do not meet all eligibility criteria where the eligibility violations are mendable and found prior to device activation (e.g. missing a test at screening or not being washed off of pharmacological treatment of overactive bladder for at least two weeks prior to baseline) will be re-baselined. Subjects enrolled who do not meet eligibility criteria will still be included in the safety and efficacy analyses.

3. Study objectives and outcome measures

The G170301 study is designed to evaluate the safety and efficacy of eCoin™ tibial nerve stimulation in subjects with UUI. See Table 1 for the study objectives and outcome measures. The primary outcomes will be measured after 48 weeks of eCoin™ therapy (equivalent to 52 weeks post-implantation). The secondary outcomes will be measured at 24 weeks of eCoin™ therapy (equivalent to 28 weeks post-implantation). The primary and secondary efficacy outcome measures will be based on data collected from 3-day voiding diaries. The diaries should be completed over three consecutive days during the seven days prior to each visit. Accordingly, the primary efficacy outcome measured at the post-activation week 48 visit will be based on voiding diary data collected within 7 days prior to the week 48 visit.

Table 1. Study objectives and outcome measures

Primary effectiveness
Objective: to assess the effectiveness of eCoin™ on the proportion of responders, that is, subjects achieving at least a 50% improvement in the number of UUI episodes per 24 hours on a 3-day voiding diary after 48 weeks of therapy
Assessment of outcome: proportion of responders after 48 weeks of therapy

Key secondary effectiveness
Objective: to assess the effectiveness of eCoin™ on the proportion of responders, that is, subjects achieving at least a 50% improvement in the number of UUI episodes per 24 hours on a 3-day voiding diary after 24 weeks of therapy
Assessment of outcome: proportion of responders after 24 weeks of therapy

Primary safety
Objective: to assess safety 52 weeks after implantation of eCoin™
Outcome: device-related adverse events from implantation to 52 weeks after implantation of eCoin™

Key secondary safety
Objective: to assess safety 28 weeks after implantation of eCoin™
Outcome: device-related adverse events from implantation to 28 weeks after implantation of eCoin™

Secondary
The following secondary objectives and outcomes will be based on data after both 24 and 48 weeks from activation:
Objective: to evaluate the effectiveness of eCoin™ with respect to the following outcome measures:

- Proportion of subjects achieving 75% improvement in the number of UUI episodes per 24 hours on a 3-day voiding diary
- Proportion of subjects achieving 100% improvement in the number of UUI episodes per 24 hours on a 3-day voiding diary
- Change from baseline in the number of UUI episodes per 24 hours on a 3-day voiding diary
- Change from baseline in the number of urinary voids per 24 hours on a 3-day voiding diary in those subjects whose baseline shows more than 10 voids per day
- Change from baseline in the number of urgency episodes per 24 hours on a 3-day voiding diary
- Change from baseline in the number of nocturia episodes per 24 hours on a 3-day voiding diary
- Change from baseline in patient-reported quality of life utilizing the Overactive Bladder Symptom Quality of Life Questionnaire (OABq)
- Change in patient-reported overactive bladder condition utilizing the Patient Global Impression of Improvement (PGI-I) questionnaire
- Patient-reported satisfaction with eCoin™ therapy utilizing the custom patient satisfaction rating survey

4. Study schedule

Study visits will be conducted as presented in Exhibit 1. Study day is presented in reference to the device initial activation (“Day 1”). The enrollment process consists of screening (including obtaining written consent), completing the baseline evaluation, implanting the eCoin™ system, and establishing the participant’s amplitude setting. Subjects will return two weeks after implantation for an incision healing check (Visit 4). The eCoin™ device will be activated four weeks after implantation (Visit 5). Follow-up assessments will occur at 4 (Visit 6), 8 (Visit 7), 12 (Visit 8), 24 (Visit 9), 36 (Visit 10), and 48 (Visit 11) weeks post-activation. Re-programming visits will occur at 8 (Visit 7b), 24 (Visit 9b), and 36 (Visit 10b) weeks post-activation. The device explant visit (Visit 12) will occur between 0 and 15 days from Visit 11 and a final incision healing check (Visit 13) will occur 2 weeks post-explantation.

Exhibit 1. Schedule of visits

Procedure	Screening (Visit 1)	Base-line (Visit 2)	Implant procedure (Visit 3)	Incision healing check (Visit 4)	Initial activation (Visit 5)	Visit 6	Visit 7	Visit 7b	Visit 8	Visit 9	Visit 9b	Visit 10	Visit 10b	Primary endpoint (Visit 11)	Explant visit (Visit 12)	Incision healing check (Visit 13)
	Day -106 to -33	Day -78 to -30	Day -43 to -23	Day -34 to -4	Day 1	Day 23 to 33	Day 51 to 61	Day 51 to 68	Day 79 to 89	Day 163 to 173	Day 163 to 180	Day 247 to 257	Day 247 to 264	Day 331 to 341	Day 331 to 356	Day 340 to 375
Informed consent	X															
Urinalysis	X															
Post void residual (PVR)	X															
Demographics, screening exam, physical exam, and medical history	X															
Vital signs ^a	X	X	X	X		X	X		X	X		X		X		X
Eligibility determination	X	X														
Concomitant medications	X	X	X	X	X	X	X	X	X	X	X	X	X	X	X	X
Adverse events	X	X	X	X	X	X	X	X	X	X	X	X	X	X	X	X
3-day voiding diary ^b		X	X			X	X		X	X		X		X		
OABq assessment		X	X			X	X		X	X		X		X		
TENS instructions		X														
Patient reported satisfaction assessment ^c			X			X	X		X	X		X		X		
Patient global impression of improvement ^c			X			X	X		X	X		X		X		
Return of TENS unit			X													
Implant or explant procedure			X												X	
Incision assessment				X												X
Activation / re-programming					X			X			X		X			
Completion of study																X

a. Weight, height, body mass index, temperature, pulse rate, respiratory rate, and blood pressure will be assessed at the screening visit. Only pulse rate, temperature, and blood pressure will be collected at subsequent visits. In addition, respiratory rate will be collected at visit 4 and visit 13.
b. For visits involving a 3-day diary, the diary should be completed over 3 consecutive days during the 7 days prior to each indicated visit. The site should give patients a telephone call to remind them of the diary requirement at least 3 days prior to each follow-up visit.
c. Visit 3 (Implant procedure) will assess satisfaction and impression of improvement relative to the TENS therapy. All other visits will be relative to the eCoin™ neuromodulation device.

5. Analysis populations

Effectiveness analyses will be generated for all analysis populations described below. Safety data will be reported on all enrolled subjects who undergo a procedure for implantation of the study device.

5.1. Intent-to-Treat (ITT)

The intent-to-treat (ITT) population will consist of all enrolled subjects who undergo a procedure for implantation of eCoin™. This is the primary analysis population for the safety and effectiveness analyses.

5.2. Modified Intent-to-Treat (mITT)

The modified intent-to-treat (mITT) population will consist of all eligible subjects in the ITT population.

5.3. OAB drug-free

The OAB drug-free population will include all subjects in the mITT population who took no medication for OAB during the study period.

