The primary sample size target is 120 subjects having UUI. For enrollment, eligible subjects will be consented and entered into a baseline evaluation period to confirm study eligibility. Baseline assessment will include complete medical history, physical examination, and completion of a 3-day voiding diary to quantify voiding behavior, symptoms, and incontinence. Only subjects who meet all the inclusion and exclusion criteria, and have provided informed consent, will be enrolled.

All eligible enrolled subjects will be scheduled to be implanted with the eCoin[™] system after baseline assessment. The investigator will select the side of implantation. Approximately 4 weeks post implantation, subjects will return for a programming visit at which time the device will be activated. A programming technician will implement the activation procedure, setting amplitude of stimulation according to the upper level of a subject’s comfort.

3-3-2-2 Selection Criteria

Participants shall be screened in accordance with the following inclusion and exclusion criteria.

3-3-2-2-1 Inclusion Criteria

1. Women and men between 18 and 80 years old.
2. Diagnosis of overactive bladder with urgency urinary incontinence or mixed urge and stress incontinence with a predominant urgency component (self-reported), for at least 6 months.
3. Individual has at least one urgency urinary incontinence episode on each of three days as determined on a 3-day voiding diary.
4. Individual gives written informed consent.
5. Individual is mentally competent and able to understand all study requirements.
6. Individual is willing and able to complete a 3-day voiding diary and quality of life questionnaire.

Pivotal Study of Subcutaneous Tibial Nerve Stimulation with eCoin[®] for Urgency Urinary Incontinence.

7. Individual is without pharmacological treatment of overactive bladder (antimuscarinics and β 3-adrenoceptor agonists) for 2 weeks prior to baseline or longer if the investigator judges that the therapeutic effect is still present.
8. Individual is intolerant of or has an inadequate response to any of anticholinergics, β 3-adrenoceptor agonists, onabotulinumtoxinA, or percutaneous tibial nerve stimulation.

3-3-2-2-2 Exclusion Criteria

1. Individual has predominantly stress urinary incontinence with more than 1/3 stress urinary incontinent episodes when compared to total urinary incontinent episodes.

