The ordered enrollment process consists of screening (including obtaining written consent), completing the baseline evaluation, implanting the eCoin[™] system, and establishing the participant's amplitude setting. This Section includes a table of the visit schedule and contents thereof. The timing of visits 1 through 4, 12 and 13, is described in relationship to the visit named, while the timing of visits 6 through 11 is described in relationship to the initial activation visit (Visit 5). A revision procedure would not reset the initial activation date.

For visits involving a 3-day diary, the diary should be completed over 3 consecutive days during the 7 days prior to each indicated visit. The site should give patients a telephone call to remind them of the diary requirement at least 3 days prior to each follow-up visit.

- Visit 1: Screening Procedures (informed consent, urinalysis, PVR, history and physical examination, subjects begin 2 week wash-off of OAB medications if applicable, concomitant medication therapy review, eligibility determination)
- Visit 2: Baseline Assessments (3-day voiding diary, OABq, subject receive TENS instructions, final eligibility determination) (Time: Between 3 and 28 days from Visit 1)
- Visit 3: Implant Procedure (Return of 3-day voiding diary completed alongside TENS, adverse event assessment, concomitant therapy review, patient surveys including OABq, patient satisfaction, and patient global impression of improvement, return of the TENS unit, pre and post-op pictures) (Time: Between 7 and 35 days from Visit 2)
- Visit 4: Incision Healing Check (week 2) (Time: Between 9 and 19 days from Visit 3) including pictures
- Visit 5: Initial Activation (week 4) (Time: Between 23 and 43 days from Visit 3) including pictures
- Visit 6 (4 weeks post-activation): Follow-up Assessments (3-day voiding diary, adverse event assessment, concomitant medication therapy review, patient surveys including OABq, patient satisfaction, and patient global impression of improvement) (Time: Between 23 and 33 days from Visit 5)
- Visit 7 (8 weeks post-activation): Follow-up Assessments (3-day voiding diary, adverse event assessment, concomitant medication therapy review, patient surveys including OABq, patient satisfaction, and patient global impression of improvement) (Time: Between 51 and 61 days from Visit 5)

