- 3) Assessments at visits 4, 8, 12, 24, 36, and 48 weeks post-activation contain the same procedures. They are described in the Visit Overview Section 3-4-2. The 8, 24, and 36 week visits will include a scheduled reprogramming to check in on how the patient is doing with the device settings.
- 4) All other visits are also described in the Visit Overview Section 3-4-2.

At the follow-up visit 48 weeks post-activation, the primary effectiveness endpoint will have been reached.

3-4-12 Escape Procedure

Unless judged medically necessary, medications for overactive bladder are not allowed until the primary effectiveness endpoint is reached at 48 weeks post activation. Agents added or withdrawn are at the discretion of the Investigator and managing physician. Any such adjustment is to be noted on the CRFs. Patients are also asked at each follow-up visit whether they have taken any medication for overactive bladder. Any answer of “yes” will be reported on the visit CRF and a corresponding concomitant medication CRF.

3-5 Study Objectives

3-5-1 Primary and Key Secondary Objectives

3-5-1-1 Primary Effectiveness Objective

To assess the effectiveness of eCoin[™] on the proportion of subjects achieving at least a 50% improvement in the number of urgency urinary incontinence episodes per 24 hours on a 3 day voiding diary after 48 weeks of therapy.

3-5-1-2 Key Secondary Effectiveness Objective

To assess the effectiveness of eCoin[™] on the proportion of subjects achieving at least a 50% improvement in the number of urgency urinary incontinence episodes per 24 hours on a 3 day voiding diary after 24 weeks of therapy.

3-5-1-3 Primary Safety Objective

To assess safety 52 weeks after implantation of eCoin[™].

Pivotal Study of Subcutaneous Tibial Nerve Stimulation with eCoin[®] for Urgency Urinary Incontinence.

3-5-1-4 Key Secondary Safety Objective

To assess safety 28 weeks after implantation of eCoin[™].

3-5-2 Secondary Objectives

The following objectives refer to measures taken after 24 and 48 weeks of therapy.

To assess the proportion of subjects achieving 75% improvement in the number of urgency urinary incontinence episodes per 24 hours on a 3 day voiding diary.

To assess the proportion of subjects achieving 100% improvement in urgency urinary incontinence episodes (“Dryness”) per 24 hours on a 3 day voiding diary.

To assess the reduction in the number of urgency urinary incontinence episodes per 24 hours on a 3 day voiding diary.

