Rate: 20 pulses per second (fixed)

Pulse Width: 0.2 ms (fixed)

Treatment Duration: 30 Minutes (fixed)

Treatment Interval: 3 days for the first 18 weeks (42 sessions) and every 4 days thereafter (fixed)

[figure not shown]
3-8-3 Implant Procedure

Subcutaneous implantation of the eCoin[™] is done under local anesthesia. The most prominent point of the medial malleolus will be palpated and marked. With the foot positioned at a 90-degree angle, a second marking is made 3 cm posterior to the medial malleolus marking. The implantation target location is found 3 cm cephalad to this second point along a line parallel to the posterior margin of the calcaneal tendon. Continuing on this line, the incision is made 8 mm cephalad to the target implantation site. The incision is made to the depth of the fascia with a width slightly smaller than that of the eCoin[™]. Then, the eCoin[™] is slid on top of the fascia until it reaches the

Original Application for an Investigational Device Exemption

Pivotal Study of Subcutaneous Tibial Nerve Stimulation with eCoin[®] for Urgency Urinary Incontinence.

implantation site. The incision is then closed and dressed. See Attachment 4-2 for a complete surgical implant manual.

3-8-4 Activation of eCoin[™] System

After a 4 week period of implant healing, the eCoin[™] devices are activated with the stimulation amplitude set to the subject's upper most comfortable level. Once activated, the eCoin[™] applies a 30 minute session of neuromodulation therapy at the programmed amplitude every 3 days for a 18 week period and then every 4 days thereafter. All subjects are activated and the schedule of therapeutic sessions is automated as discussed.

3-8-5 Subject Compliance Monitoring

eCoin[™] Therapy: Neuromodulation therapy is provided automatically by the implant system and has no compliance requirements.

Drug Therapy: Subjects will be asked whether they are taking an overactive bladder medication through the primary endpoint to confirm that subjects are free of overactive bladder medication.

Data: Compliance with voiding diaries is established through review by the clinical study coordinator at each center.

Appointment Compliance: Clinics' designated study coordinators will ensure subjects are compliant with study appointments within the scheduling parameters outlined in the Visit Overview described in Section 3-4-2.

Pivotal Study of Subcutaneous Tibial Nerve Stimulation with eCoin[®] for Urgency Urinary Incontinence.

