10.4.2. Additional OAB medications

Medications for OAB are not allowed until the primary effectiveness endpoint is reached at 48 weeks post-activation, unless judged medically necessary. Any subjects who have taken OAB medications will be included in the primary effectiveness outcome variable analysis. OAB medication use will be reported alongside the primary analysis. The timing of OAB medications will be displayed, including duration of treatment, start and end dates, and dosage.

The following additional sensitivity analyses may be performed.

- For the primary effectiveness outcome variable at week 48, data for subjects who have taken OAB medications while on study will be considered missing and imputed assuming they had not taken any OAB medication.
- For weeks 4, 8, 12, 24, 36, and 48, 2 different sets of analyses will be performed.
 - *While on OAB medication.* Subjects will be imputed as non-responders while they are taking OAB medication.
 - *Any OAB medication.* A very conservative set of analyses will consider a subject a non-responder at every visit after she starts OAB medication.

For example, no matter what subjects write on their diaries, the “while on OAB medication” analyses will consider subjects as non-responders from week 12 through week 36 if they take OAB medication at week 12 and stop that medication at week 36. The “any OAB medication” analyses will consider such subjects non-responders from week 12 through week 48.

11. Safety summaries

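### The OAB drug-free set, the use reported beside the primary result and the optional co-treatment sensitivity analyses respond only to OAB medication, so PTNS, TENS or onabotulinumtoxinA given with eCoin in place counts as no co-treatment.

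*SAP*

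**What the plan says.** Three planned outputs deal with treatment for overactive bladder (OAB) taken on top of eCoin.

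- **Analysis set.** The OAB drug-free set (SAP 5.3; protocol 3-9-3-2) is "all subjects in the mITT population who took no medication for OAB during the study period". The per-protocol set is cut from it (SAP 5.4), and SAP 10.4 repeats the efficacy analyses in both.
- **Reporting.** SAP 10.4.2 and protocol 3-9-7-1 state: "OAB medication use will be reported alongside the primary analysis". Duration, dates and dosage are to be shown.
- **Sensitivity analyses.** These are optional: "The following additional sensitivity analyses may be performed". One treats week-48 data of medication users as missing and imputes them. The *while on* version says "Subjects will be imputed as non-responders while they are taking OAB medication". The *any* version makes a subject a non-responder at every visit after OAB medication starts.

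The questions put to subjects are also about drugs. Protocol 3-4-12 says "Patients are also asked at each follow-up visit whether they have taken any medication for overactive bladder", and protocol 3-8-5, under its drug-therapy item, says "Subjects will be asked whether they are taking an overactive bladder medication through the primary endpoint". Follow-up visits do, however, include a broader item (protocol 3-4-2): "adverse event assessment, concomitant medication therapy review, patient surveys including OABq".

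At entry the protocol looks beyond drugs. Its exclusion criteria cover PTNS in the previous 4 weeks (or longer by investigator judgement), current TENS of the pelvic region, back or legs, any prior sacral nerve stimulation, and onabotulinumtoxinA in the previous 9 months.

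**The concern.** The entry criteria treat non-drug OAB therapies and onabotulinumtoxinA as things that could distort the measured response. After implantation, the outputs meant to show whether the response depends on co-treatment no longer mention them. With no control arm, those outputs are the planned way to answer that question, and as worded they answer it for drugs only.

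Such use is conceivable. Inclusion criterion 8 recruits people who failed or could not tolerate drugs, onabotulinumtoxinA or PTNS. Protocol 3-3-3 keeps subjects without benefit in follow-up. Protocol 3-4-7 teaches every subject tibial TENS before implantation. A week-48 responder who had added one of these therapies would sit in the drug-free set and would not appear in the co-treatment report.

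**Working it through.** **Step 1. Compare each rule with its trigger.**

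| Rule | Source | Trigger | Reaches PTNS, TENS or sacral stimulation with eCoin in place? |
|---|---|---|---|
| OAB drug-free set | SAP 5.3; protocol 3-9-3-2 | OAB medication | No |
| Reporting beside primary result | SAP 10.4.2; protocol 3-9-7-1 | OAB medication | No |
| Imputed week 48, *while on*, *any* | SAP 10.4.2; protocol 3-9-7-1 | OAB medication | No |
| Concomitant therapy summary | SAP 8.5 | Defined as any therapy other than eCoin, but the output is medications by generic name | Not in the output |
| Explant rule | SAP 10.1 | Device removed, other than for MRI | No; the device stays in |
| Per-protocol set | SAP 5.4 and 8.2 | Major deviation, defined generically | Only if so judged |

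**Step 2. Where does onabotulinumtoxinA fall?** Inclusion criterion 7 spells out pharmacological OAB treatment as antimuscarinics and beta-3 agonists, to be stopped "for 2 weeks prior to baseline or longer if the investigator judges that the therapeutic effect is still present". Protocol 3-3-3 mentions botulinum toxin alongside sacral neuromodulation and apart from drug therapy. SAP 8.3 lists Botox separately from OAB medications. All three suggest that it lies outside the drug rules.

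**Step 3. Reproduce the plan's own interval.** The Clopper-Pearson lower bound for x responders of n is the 2.5% quantile of Beta(x, n − x + 1).
- 60/120: 0.407, matching 0.41 in SAP Table 2.
- 66/120: 0.4565, matching 0.46 at an observed 0.55.
- 59/120: 0.399. The success rule therefore needs at least 60/120.

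**Step 4. Illustrate the size.** The documents give no rate of non-drug co-treatment. Assumptions: n = 120, 66 diary responders (55.0%), 1 to 5 users, no OAB drug users, and everyone eligible so that the drug-free set starts at 120. The last is a simplification, since SAP 2.5 reports several ineligible subjects implanted at one center.

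| Scenario | 1 user | 5 users |
|---|---|---|
| Recode as non-responder, all users respond | 65/120 = 54.2%, lower bound 44.8% | 61/120 = 50.8%, lower bound 41.6% |
| Recode as non-responder, no user responds | 66/120 = 55.0%, lower bound 45.6% | the same |
| Remove from set, all users respond | 65/119 = 54.6%, lower bound 45.2% | 61/115 = 53.0%, lower bound 43.5% |
| Remove from set, no user responds | 66/119 = 55.5%, lower bound 46.1% | 66/115 = 57.4%, lower bound 47.8% |

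As the plan is worded, under these assumptions both outputs stay at 66/120 in every scenario. The imputed week-48 analysis cannot be illustrated without data.

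**Step 5. How far does this depend on the 66?** From 66/120, seven responding users would have to be recoded before the bound fell below 40% (66 − 7 = 59; lower bound 0.399). From 60/120, one would be enough. Either way it is the sensitivity analysis that moves, not the success rule.

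**The case against.** The strongest reply is that the plan has a route for these therapies. OAB drug use is expressly a minor deviation (SAP 2.3 and 8.2), so the deviation route would not remove drug users and they needed their own set. PTNS or sacral stimulation added to a tibial-nerve trial could well be judged to affect scientific validity. That would make it a major deviation and remove the subject from the per-protocol set, in which efficacy is re-analysed. This stands in part, so a reader should not infer that no planned analysis can act on such use. But neither document names these therapies as deviations or bans them after implantation, and the other outputs would still count the subject as free of co-treatment.

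Second, medication is the only co-treatment the protocol provides for, through its escape procedure, so a drug-only scope follows the design. That explains the wording but does not close the gap.

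Third, a reader might infer that non-drug therapy goes unrecorded. The documents do not show that. Visits include a concomitant medication therapy review, and the case report forms and the COVID-19 addendum to the SAP are not in the supplied text.

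Fourth, a reader might infer that two analysts would classify onabotulinumtoxinA differently. Step 2 makes that weak, because the three places agree.

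Fifth, sacral stimulation with eCoin still in place is unlikely, and a subject explanted in order to switch is already a non-responder. This stands, and the case rests mainly on PTNS, TENS and onabotulinumtoxinA.

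**Conclusion.** The point holds as a minor one. The drug-free set, the reporting beside the primary result and the optional sensitivity analyses speak only to drug co-treatment. A subject with PTNS, TENS or onabotulinumtoxinA on top of eCoin, and no OAB drug, passes through them as free of co-treatment. This rests on the wording of both documents, which agree.

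The size is unknown. In the assumed range the recoded rate falls by at most 4.2 points (55.0% to 50.8%). The drug-free rate can move either way, between 53.0% and 57.4%. No lower bound falls below 40%, but that depends on the assumed 66/120.

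It is tempting to go further and say that uncaptured co-treatment could produce a false success. The documents do not support that. The primary analysis counts week-48 diaries whatever the co-treatment, its rule is unchanged by this point, and no rate of use is given from which to compute such a risk.

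**What to change.** Before database lock, which SAP 7.3 allows, amend SAP 10.4.2 and protocol 3-9-7-1.

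- **Report** beside the primary result any OAB treatment other than eCoin received from implantation to the week-48 diary: antimuscarinics, beta-3 agonists, onabotulinumtoxinA, PTNS, TENS of the pelvic region, back or legs, and sacral neuromodulation. Counting from implantation leaves out the protocol's own 7-day TENS run, which comes before it.
- **Use the same list** to trigger the imputed week-48 analysis and the *any* non-responder analysis, and to define exclusion from the drug-free set (SAP 5.3; protocol 3-9-3-2). The per-protocol set follows, because it is cut from that set.
- **Leave the *while on* analysis** for medications as written. For injections and treatment sessions it would need new carry-over windows. The entry washouts (9 months for onabotulinumtoxinA, for example) were not set for that purpose, and borrowing them would be debatable.
- **For visits already held**, take the information from the concomitant therapy review and source records.

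The primary analysis and permitted care stay unchanged. The main cost is wording. Enrolment was due to finish by March 2019 and the SAP is dated 28 August 2019, so capture of non-drug therapy at past visits may be incomplete. The drug-free and per-protocol sets may lose a few subjects, and sensitivity response rates may fall slightly.
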